## SUMMARY OF CHANGES

Protocol Date	Section	Change
11/4/2019		Initial IRB approval reviewed on 11/26/19
1/16/2020		Revised protocol (version 1) for Initial IRB approval
2/4/2020		Revised protocol (version 2) for Initial IRB approval
6/10/21		Revised protocol (version 3) Dosimetry and volumetry results from an earlier pilot series of 8 cases (IRB#17-823 Effect of PET/MR Attenuation correction in Y90 dosimetry analysis compared to PET/CT); will be compared to verify their consistency and evaluate the validity of using them interchangeably and will be included in the statistical analysis

## PROTOCOL SUMMARY

12 consecutive cases undergoing yttrium-90 radioembolization (Y-90 RE) for hepatic malignancies at our institute are consented to participate at this trial. Within 6 hours after the procedure, the patients undergo PET/CT and PET/MR imaging (less than 1 hour apart) for evaluation of the treatment and software-assisted measurement of yttrium-90 absorbed doses in the tumor and surrounding liver tissue. Dosimetry data acquired from the two imaging modalities from these cases, in addition to the post-Y90 RE dosimetry and volumetry results from an earlier pilot series of 8 cases (IRB#17-823 Effect of PET/MR Attenuation correction in Y90 dosimetry analysis compared to PET/CT; similar protocol design), will be compared to each other to verify their consistency and evaluate the validity of using them interchangeably.

## ABBREVIATIONS

CT	Computed Tomography
DSMP	Data and Safety Monitoring Plan
GCP	Good Clinical Practice
HIPAA	Health Information Portability and Accountability Act
ICH	International Conference on Harmonization
IEC	Independent Ethics Committee
IRB	Institutional Review Board
MRI	Magnetic Resonance Imaging
PET	Positron Emission Tomography
RDC	Reproducibility Coefficient
RE	Radioembolization
SD	Standard Deviation
SIRT	Selective Internal Radiation Therapy
SPECT	Single Photon Emission Computed Tomography

### **REFERENCES**

## **1.0 INTRODUCTION**

### **1.1 Selective Internal Radiation Therapy**

The liver is one of the most common sites for metastatic diseases. Moreover, primary cancers in the liver are a major global matter of concern, with incidence rates that have increased substantially within the past two decades [1]. Selective internal radiation therapy (SIRT) with yttrium (Y)-90 is a well-established modality for palliative treatment of primary and metastatic liver malignancies and constitutes delivery of radioactive-emitting embolic microspheres through selection of arteries that directly feed the tumor. Radioembolization (RE) through this method achieves prolonged patient survival with limited systemic adverse effects and acceptable safety profile [2, 3].

### **1.2 Post Y-90 Radioembolization Imaging**

Various imaging modalities including single-photon emission computed tomography (SPECT) and positron emission tomography (PET), in combination with computed tomography (CT) or magnetic resonance imaging (MRI), are incorporated as part of standard patient care after Y-90 RE to evaluate the distribution of radionuclide particles within the liver (and elsewhere in the body) and to calculate the radionuclide absorbed doses in the tumors, which in turn would permit optimal planning for continuation of patient's care [4]. Accurate tumor Y-90 dosimetry is crucial for determination of the treatment efficacy and prediction of the response to therapy. In comparison to SPECT, post-Y-90 RE imaging with PET/CT has been proven to serve as a favorable modality for this purpose as it delivers better spatial resolution and higher precision in quantifying tumor absorbed doses. These advantages improve Y-90 RE treatment planning by generating more pertinent dose-response and dose-toxicity data [5]. Hence, Y-90 PET/CT has become the modality of choice for post-Y-90 RE imaging in many centers across the US including our institute. Y-90 PET/MR is another imaging modality that may be performed after SIRT with Y-90 and confers superior soft tissue contrast and determination of the liver/tumor contours, compared to Y-90 PET/CT imaging [6]. For this reason, post-Y-90 RE PET/MR is frequently performed at our institute, encompassing over 200 cases since 2016. Despite this, Y-90 PET/CT still provides a better quantification of PET images, due to the better attenuation correction, and remains as the gold standard method [6]. This necessitates assessment of the validity of dosimetry results acquired by Y-90 PET/MR, in comparison to PET/CT imaging.

### **1.3 Rationale of Study**

In a prior pilot study to compare post-Y-90 RE dosimetry results between PET/CT and PET/MR imaging, the current investigators observed significant inconsistencies

between the two modalities; in other words, tumor absorbed doses were on average 36% (SD = 43%) lower in PET/MR-based calculations than in PET/CT [7]. This resulted in PET/MR software upgrades which predominantly included a few improvements in the attenuation correction as well as the respiratory motion correction methods. In order to validate these PET/MR-based dosimetry upgrades, this protocol was designed including another pilot trial of 8 cases, to compare Y-90 dosimetry data between PET/CT and PET/MR. Given the promising results of the second pilot trial (IRB#17-823 Effect of PET/MR Attenuation correction in Y90 dosimetry analysis compared to PET/CT), the investigators are proposing this study (with similar design) to extend their research on more cases.

## **2.0 OBJECTIVE**

### **2.1 Primary Objective**

To assess the agreement between post-Y-90 RE absorbed doses (Gy) in the liver tumor tissues based on PET/CT versus PET/MR imaging. This objective would permit the comparison of Y-90 tumor absorbed doses, acquired from PET/MR, with the current standard of care PET/CT imaging to verify the data consistency and to validate its application for the prediction of tumor response to treatment. The endpoint for this objective would be the measurement of the reproducibility coefficient (RDC) between the two imaging modalities for post-Y-90 RE absorbed doses (Gy) in the liver tumor tissues (please see the Study Design for further details).

### **2.2 Secondary Objective**

To assess the agreement between post-Y-90 RE absorbed doses (Gy) in the background liver tissues (surrounding tumors), based on PET/CT versus PET/MR imaging. This objective would permit the comparison of Y-90 background liver absorbed doses, acquired from PET/MR, with the current standard of care PET/CT imaging to verify the data consistency and to validate its application for the prediction of dose toxicity. The endpoint for this objective would be the measurement of the RDC between the two imaging modalities for post-Y-90 RE absorbed doses (Gy) in the background liver tissues (please see the Study Design for further details).

## **3.0 STUDY DESIGN**

### **3.1 Number of Subjects**

Upon IRB approval and patient's informed consent, 12 new consecutive cases will be enrolled in the study. The sample size calculation ( $n = 12$ ) is based on the fact that the

RDC should be  $\leq 5\%$  for clinical use. The following table summarizes the estimated upper 95% confidence bound for the RDC as a function of the unknown RDC. Based on this table and our expectation that our new technique will have an excellent reproducibility with PET, a sample size of 12 will provide sufficient precision to determine if the RDC with our new technique is near 5%.

Estimated Upper 95% Confidence Bound for RDC

# Cases	Magnitude of RDC			
	RDC=2%	RDC=3%	RDC=4%	RDC=5%
10	3.2	4.8	6.4	8.0
12	3.0	4.5	6.1	7.6
15	2.9	4.3	5.7	7.2

[figure not shown]
### 3.2 Study Protocol

The study protocol is outlined in the diagram below. Upon the patient's informed consent and eligibility approval (according to the inclusion/exclusion criteria below) for participation in the trial, they undergo PET/CT (standard imaging) and PET/MR (additional imaging), within 6 hours after SIRT with Y-90 for palliative treatment of the liver malignancy. Patients will be randomized to receive either of the imaging modalities first, based on the availability of the imaging device, and less than 1 hour apart. This limited time threshold allows to ignore the trivial amounts of  $\beta^-$  decay in radionuclide emission that happens after trans-arterial delivery of Y-90 microspheres into the liver, with regards to its half-life of  $\sim 64$  hours. Upon acquirement and construction of PET/CT and PET/MR images, a software (MIM SurePlan LiverY90) would be utilized for semi-automatic determination of the liver/tumor contours and calculation of the Y-90 absorbed doses (Gy) in the regions of interest (including within tumor and background liver outlines) using the Local Deposition Method.

Dosimetry/volumetry data from the two modalities from these cases, in addition to the results from the pilot cases (IRB#17-823 Effect of PET/MR Attenuation correction in Y90 dosimetry analysis compared to PET/CT ; similar protocol design), will be compared using the Bland Altman method to assess the pattern of differences between dosimetry values and to measure the reproducibility of the methods [8]. The RDC is the minimum difference between the two measurements that can be considered a true difference, with 95% confidence. It will be calculated as 2.77 times the within-subject SD (wSD), where wSD is the square root of the mean variance across the N subjects, and the variance for each subject is calculated from their two dosimetry values [9,10]. In addition, the reproducibility coefficient will also be expressed as a percentage of a subject's PET/CT value of dose, using the within-subject coefficient of variation

(wCV) instead of wSD. An upper 95% confidence bound for the RDC will be constructed using a chi square statistic as the pivotal statistic, as follows:

$$2.77 \times \sqrt{N \times \%wCV^2 / \chi_{M,\alpha}^2}, \text{ where } \chi_{M,\alpha}^2 \text{ is the } \alpha\text{th percentile of the chi square distribution with } N \text{ degrees of freedom.}$$

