### 4.2 Exclusion Criteria

- A) The patient loses competence, has a condition that questions their ability to provide informed consent independently (e.g. cannot communicate in English), or withdraws consent to participate within any time in the study period; OR
- B) The patient is not eligible to undergo MRI due to the presence of metal devices or implants in their body; OR
- C) Both imaging modalities cannot take place within 6 hours after Y-90 RE; OR
- D) Both imaging modalities cannot take place within 1 hour apart from each other

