## **7.0 RECORDS TO BE KEPT/REGULATORY CONSIDERATIONS**

### **7.1 Data Reporting**

The OnCore™ Database would be utilized, as required by the Case Comprehensive Cancer Center, in order to provide data collection for both accrual entry and trial data management. OnCore™ is a Clinical Trials Management System housed on secure servers maintained at Case Western Reserve University. Access to data through OnCore™ is restricted by user accounts and assigned roles. Once logged into the OnCore™ system with a user ID and password, OnCore™ defines roles for each user which limits access to appropriate data. User information and password can be obtained by contacting the OnCore™ Administrator at [contact].

OnCore™ is designed with the capability for study setup, activation, tracking, reporting, data monitoring and review, and eligibility verification. This study would utilize electronic Case Report Form completion in the OnCore™ database. A calendar of events and required forms are available in OnCore™.

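### Scan order is called randomized but follows scanner availability, and decay between scans is dismissed as trivial; if left uncorrected, that decay is not negligible against the 5% RDC criterion

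*Combined protocol and SAP*

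**What the plan says.** On scan order, Section 3.2 (Study Protocol) states: "Patients will be randomized to receive either of the imaging modalities first, based on the availability of the imaging device". The text gives no sequence, ratio or random mechanism. The study diagram is not available in the copy reviewed.

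On decay, Section 3.2 continues: "This limited time threshold allows to ignore the trivial amounts of" beta decay, citing a half-life of about 64 hours. The time limit recurs in the Protocol Summary ("the patients undergo PET/CT and PET/MR imaging (less than 1 hour apart") and in Section 4.2, which excludes a patient if "Both imaging modalities cannot take place within 1 hour apart from each other". None of these places says whether the gap runs from start to start or from the end of one scan to the start of the next.

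On the endpoint, Section 2.1 states: "The endpoint for this objective would be the measurement of the reproducibility coefficient (RDC) between the two imaging modalities". Section 3.2 defines the RDC as 2.77 times the within-subject SD, where "the variance for each subject is calculated from their two dosimetry values". Section 3.1 says the RDC should be at most 5% for clinical use and that "a sample size of 12 will provide sufficient precision to determine if the RDC with our new technique is near 5" percent.

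On data capture, Section 7.1 says "A calendar of events and required forms are available in" OnCore. The protocol text does not itself name scan order or scan start times as data items.

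**The concern.** The two statements in Section 3.2 bear on each other. The scan done second sees slightly less activity. If that loss is not corrected, it enters the paired dose difference with a sign set by scan order. The RDC is built from squared paired differences, and no mean difference between modalities is removed first, so both the decay and any modality bias count in it.

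The 1-hour limit caps the decay but does not remove it. Section 3.2 judges the decay against the half-life and does not compare it with the 5% tolerance on the primary endpoint. An order driven by availability may be unbalanced, and then decay and modality bias mix. At stake are a modest distortion of the primary endpoint and a report that describes a convenience order as randomized.

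**Working it through.** **Inputs.** Half-life 64 h, gap up to 1 h and multiplier 2.77 (Section 3.2); criterion 5% and N = 12 (Section 3.1); 12 new plus 8 pilot cases = 20 pooled (Protocol Summary). Assumptions: no existing decay correction, gaps measured start to start, and differences expressed as a percentage of dose.

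**The plan's own figure.** Upper bound = RDC × √(N / χ²(0.05, N)). At N = 12 the factor is 1.515, so RDCs of 2, 3, 4 and 5% give 3.03, 4.55, 6.06 and 7.58. This matches the table in Section 3.1 (3.0, 4.5, 6.1, 7.6). At N = 20 the factor is 1.358.

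**Decay.** d = 1 − 2^(−t/64): 0.540% at 30 minutes and 1.077% at 60 minutes.

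**Effect on the RDC.** The variance of two values is half their squared difference, so RDC = (2.77/√2) × RMS difference = 1.959 × RMS difference. Let b be the PET/MR minus PET/CT bias, sd the SD of the paired differences, and p the share scanned with PET/MR first. Then

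RDC = 1.959 × √(sd² + b² + d² + 2bd(2p − 1)).

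Decay alone gives 1.959 × 0.540 = 1.06% at 30 minutes and 1.959 × 1.077 = 2.11% at 60 minutes.

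**Case 1: no modality bias.** The cross term is zero, so RDC′ = √(RDC² + (1.959d)²) at any order split.

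| Decay-free RDC | 30 min | 60 min |
|---|---|---|
| 3.0% | 3.18% | 3.67% |
| 5.0% | 5.11% | 5.43% |
| Upper bound for RDC 3%, N = 12 (4.55%) | 4.82% | 5.56% |
| Upper bound for RDC 3%, N = 20 (4.07%) | 4.32% | 4.98% |

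The decay-free RDC that reaches exactly 5% is √(25 − 1.06²) = 4.89% at 30 minutes and √(25 − 2.11²) = 4.53% at 60 minutes. With zero bias, therefore, decay carries the RDC past 5% only from 4.89–5.0% or 4.53–5.0% respectively.

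**Case 2: modality bias present, 60 minutes.** The values of b and sd are assumed, because the bias after the software upgrade is not given.

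With b = −2% and sd = 2%:
- Decay-free: 1.959 × √(4 + 4) = 5.54%.
- PET/CT always first: 1.959 × √(8 + 1.16 + 4.31) = 7.19%.
- Balanced order: 1.959 × √(8 + 1.16) = 5.93%.
- PET/MR always first: 1.959 × √(8 + 1.16 − 4.31) = 4.31%.

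With b = −1.5% and sd = 1.5%:
- Decay-free: 1.959 × √4.5 = 4.16%.
- PET/CT always first: 1.959 × √(4.5 + 1.16 + 3.23) = 5.84%.

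The 5% line can thus be crossed downwards (5.54 to 4.31) or upwards (4.16 to 5.84).

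**Mean difference.** The shift is d × (2p − 1). At 60 minutes it is 1.08% if all patients have one order, 0.54% at a 9:3 split and 0 at 6:6.

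**The case against.** The strongest reply is that the decay part is not established. The sentence in Section 3.2 can be read as justifying the 1-hour limit, without instructing anyone to omit a correction. If the reconstruction or dosimetry software references activity to a common time, the effect is about zero. The investigators plainly considered decay: they gave the half-life and enforced a cap. Applying the time limits in Section 4.2 also requires knowing when the scans took place, which reveals their order, and the OnCore forms may hold those times. Finally, the effect matters only if agreement comes near 5%. With the first pilot's mean difference of 36% and SD of 43% (Section 1.3), 60 minutes of decay in balanced order moves the RDC only from 109.84% to 109.86%.

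Most of this stands. It makes the decay part conditional, and it weakens any complaint that scan times are unrecorded. It does not answer the wording on randomization. It also leaves the sponsor expecting an RDC near or below 5%, where 2.1 points from decay alone is not trivial, while the only statement on decay is that it may be ignored.

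A reader might infer that uncorrected decay inflates the RDC whatever the scan order. That holds only with zero modality bias. With bias, a balanced order still gives inflation, but an unbalanced order can deflate the RDC, as Case 2 shows. The only documented bias, from before the upgrade, is not zero.

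**Conclusion.** The point holds as a minor one, in two parts of different strength.

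The wording on randomization is inaccurate on the face of Section 3.2, and this needs no assumption.

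The decay part is conditional on activity not already being referenced to a common time. Under that condition, at gaps of 30 to 60 minutes:
- Decay alone is worth 1.1% to 2.1% of RDC.
- With no modality bias, an RDC of 3.0% becomes 3.2% to 3.7%, and 5.0% becomes 5.1% to 5.4%.
- With bias and unbalanced order, the RDC can move across 5% in either direction. The size depends on a bias that the documents do not give.

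Two further inferences are not supported. The crossing ranges (4.89–5.0% and 4.53–5.0%) are not general limits; they apply only with zero bias. Nor can it be said that the 5% criterion excludes the upper confidence bound: Section 3.1 states the criterion for the RDC, justifies the sample size with upper bounds, and gives no formal decision rule.

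All figures take the gap as start to start. If the limit means end to start, the gap between starts could exceed 60 minutes and the effect would be larger.

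**What to change.** 1. Replace the sentence on ignoring decay in Section 3.2 with: *Both scans are decay-corrected to one common reference time, using recorded scan start times, before dose differences and the RDC are computed.* Alternatively, confirm that the software already does this. Apply it to the 12 new cases and to the pilot cases whose times can be retrieved. This removes the decay term and its interaction with bias at any order split.
2. Delete *randomized* and state that order follows device availability. To keep the word, use a pre-generated 1:1 order list and document deviations.
3. Record the actual order and report the mean PET/MR minus PET/CT difference by order as a descriptive check.
4. State whether the 1-hour limit is measured start to start.

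The cost is two time stamps per patient, one correction step and a few reworded sentences, with no extra scans. Some pilot scan times may not be retrievable, which would leave up to 8 of the 20 pooled cases uncorrected. An order list, if chosen, may cause an occasional wait or a documented deviation.

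### Section 3.2 lets Y-90 decay between the two scans be ignored and names no common reference time; unless the software already corrects for it, a small but avoidable component enters the RDC

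*Combined protocol and SAP*

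**What the plan says.** Section 3.2 (Study Protocol) requires both scans within 6 hours of treatment and less than 1 hour apart. It justifies the short gap by the half-life of about 64 hours: "This limited time threshold allows to ignore the trivial amounts of" beta decay. Section 4.2 (Exclusion Criteria) repeats the limit by excluding patients for whom "Both imaging modalities cannot take place within 1 hour apart from each other". Neither section says whether the hour runs from start to start or from the end of one scan to the start of the next.

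On scan order, section 3.2 says: "Patients will be randomized to receive either of the imaging modalities first, based on the availability of the imaging device". It then assigns to a named software package the "calculation of the Y-90 absorbed doses (Gy) in the regions of interest" and does not mention a reference time for either scan.

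The RDC is 2.77 times the within-subject SD of the two doses, and is also given as a percentage through the within-subject coefficient of variation. Section 3.1 (Number of Subjects) wants it at or below 5% for clinical use and says 12 cases give "sufficient precision to determine if the RDC with our new technique is near 5" per cent. The Protocol Summary adds the new cases' data to the pilot's: "in addition to the post-Y90 RE dosimetry and volumetry results from an earlier pilot series of 8 cases". The analysis therefore has 20 cases.

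**The concern.** The later scan sees less activity than the earlier one, whichever modality comes second. If each dose is computed from the activity at its own scan time, part of the difference between the two doses is elapsed time. The RDC cannot separate that from disagreement between modalities, and the same data feed both the primary (tumor) and secondary (background liver) endpoints.

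Whether decay is trivial depends on the tolerance. About 1% is trivial beside most dosimetry errors, but here the limit is 5% and the sample-size table covers true RDCs of 2 to 5%. Scan order adds a second question. It is called randomized but follows device availability, so balance is not assured. If one modality usually goes second, decay becomes a directional difference.

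**Working it through.** **Inputs.** Half-life 64 h, gap below 1 h, and RDC = 2.77 x within-subject SD or CV (section 3.2). Limit 5% and the table of upper bounds (section 3.1). N = 12 + 8 = 20 (Protocol Summary).

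**Reproducing the plan's table.** Upper bound = RDC x sqrt(N / chi-square 5th percentile on N df). At N = 12 the factor is 1.5153. True RDCs of 2, 3, 4 and 5% give 3.03, 4.55, 6.06 and 7.58, against the printed 3.0, 4.5, 6.1 and 7.6. The rows for 10 and 15 cases also match to rounding, so the formula is understood as the plan uses it.

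**Decay over the gap.** d(t) = 1 - 2^(-t/64).
- t = 0.5 h: 0.540%
- t = 1 h: 1.077%
- t = 1.5 h: 1.611%
- t uniform on 0 to 1 h (assumption): mean 0.540%, root mean square 0.623%

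**RDC component from decay alone.** With two values per subject the within-subject SD is the difference divided by sqrt(2), so the component is 2.77 x d / sqrt(2).

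| Gap (start to start) | Component |
|---|---|
| all 0.25 h | 0.53% |
| all 0.5 h | 1.06% |
| uniform 0 to 1 h | 2.77 x 0.623 / 1.414 = 1.22% |
| uniform 0.5 to 1 h | 1.62% |
| all 1 h | 2.77 x 1.077 / 1.414 = 2.11% |
| all 1.5 h | 2.77 x 1.611 / 1.414 = 3.16% |

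The documents give no distribution of gaps, so every row is an assumption. The last row applies only if the hour is counted from the end of one scan to the start of the next, and it further assumes half an hour of scan time.

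**Effect on the observed RDC.** With no mean offset between modalities, observed RDC = sqrt(true^2 + component^2).
- True 3%: sqrt(9 + 1.22^2) = 3.24 (uniform); sqrt(9 + 2.11^2) = 3.67 (all 1 h)
- True 5%: sqrt(25 + 1.22^2) = 5.15; sqrt(25 + 2.11^2) = 5.43

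**Effect on the upper bound at N = 20.** The factor is 1.358. For a true 3% the bound goes from 4.07% to 3.24 x 1.358 = 4.40% (uniform) or 3.668 x 1.358 = 4.98% (all 1 h).

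**Effect on the Bland-Altman mean.** If one modality is always second, the mean difference shifts by the mean of d: 0.54 percentage points for uniform gaps, 1.08 if all gaps are 1 h. If there is also a real offset between modalities, simple quadrature no longer holds, and decay can add to that offset or partly cancel it.

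**If disagreement is large.** Section 1.3 (Rationale of Study) reports that, before the software upgrade, "tumor absorbed doses were on average 36% (SD = 43%) lower in PET/MR-based calculations than in PET/CT". That corresponds to an RDC of (2.77 / 1.414) x sqrt(36^2 + 43^2) = 109.8%. Adding 2.11% in quadrature gives 109.9%.

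**The case against.** The strongest reply is that the documents show no error in the endpoint. Dose calculation is left to a dedicated Y-90 package, no text says a correction is omitted, and the quoted sentence can be read as explaining the short scan window rather than as telling the analyst to skip decay correction. This stands in part: the documents cannot settle what the software does, and the effect may be zero. But the sentence does say that decay may be ignored, and no other text says that it is corrected. If correction is automatic, the justification is unnecessary; if it is not, the comparison is uncorrected.

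The second reply concerns size, and it largely stands. For uniform gaps the component is 1.22^2 / 5^2 = 6% of the squared limit. A true 3% reads about 8% higher in relative terms (3.24 / 3), while sampling error alone spreads RDC estimates at N = 20 over about -31% to +31% of the true value. None of the plan's tabulated RDCs changes side of 5% at N = 20: even with every gap at 1 h, the bounds for true 2, 3, 4 and 5% go from 2.72, 4.07, 5.43 and 6.79 to 3.95, 4.98, 6.14 and 7.37.

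A reader might set 1.2% or 2.1% beside 5% and infer that decay uses up a quarter to two fifths of the tolerance. It does not, because the components add in quadrature. A reader might also infer that decay could decide whether the method passes or fails. The plan states no pass rule on the upper bound, so the documents do not support that inference.

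**Conclusion.** The point stands at low severity. Section 3.2 permits a known time effect, unrelated to modality, to be left in the RDC, and the plan does not say whether it is in fact removed. If the software refers both scans to one time, the effect is nil. If it does not, the component is about 1.2% under uniform 0 to 1 h gaps and 2.1% with every start-to-start gap at 1 h. The 2.1% should not be read as a maximum, because the hour is undefined; an end-to-start reading allows more.

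The result rests on the assumed gap distribution, on no mean offset between modalities, and on doses being computed without correction. If present-day disagreement were still near the level before the upgrade, decay would not matter. It matters only in the 2 to 5% range for which the study was sized. The Bland-Altman shift needs one modality to be scanned second in most patients, which the order rule allows but the documents do not show.

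**What to change.** Replace the sentence in section 3.2 with: *The start time of each PET acquisition and the scan order are recorded, and both data sets are decay-corrected to the same reference time (time of Y-90 administration) before doses are compared.* If the software already does this, say so and state the reference time it uses. Apply the same correction to the 8 pilot cases where their scan times are available, and list any case that could not be corrected.

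The cost is one or two sentences, a recorded start time and one factor per scan, and a search for the pilot scan times. No extra scans or patients are needed.

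### Does section 3.2 need to list the outputs of its Bland-Altman comparison (signed mean difference, limits of agreement, intervals)?

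*Combined protocol and SAP*

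**What the plan says.** Section 3.2 (Study Protocol) states that dosimetry and volumetry data from the new cases and the pilot cases "will be compared using the Bland Altman method to assess the pattern of differences between dosimetry values and to measure the reproducibility of the methods", with a methods citation. That sentence gives two purposes.

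- **Reproducibility.** The text that follows covers this in full. The RDC is 2.77 times the within-subject SD, each subject's variance comes from the two dose values, and a percentage form uses the within-subject coefficient of variation. The interval is given as well: "An upper 95% confidence bound for the RDC will be constructed using a chi square statistic as the pivotal statistic". The interpretation is also stated: "The RDC is the minimum difference between the two measurements that can be considered a true difference, with 95% confidence".
- **Pattern of differences.** No output is listed for this purpose.

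The RDC is the sole endpoint in section 2.1 ("The endpoint for this objective would be the measurement of the reproducibility coefficient (RDC) between the two imaging modalities"), and section 2.2 repeats this for background liver. Section 3.1 sizes the study on the RDC bound, with 5% as the limit for clinical use. Section 1.2 says of PET/CT that it gives better quantification "due to the better attenuation correction, and remains as the gold standard method". Section 1.3 reports that in the first pilot, before the software upgrades, "tumor absorbed doses were on average 36% (SD = 43%) lower in PET/MR-based calculations than in PET/CT".

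**The concern.** The study follows from a directional problem: PET/MR read low, and its software was upgraded. A reader will want to know whether the deficit has gone. The RDC cannot say. It is built from squared differences, so it has no sign and adds a consistent offset to random scatter. It is also the only named endpoint and the only quantity with a written interval. If the report stopped at the RDC, a steady PET/MR under-reading and a symmetric scatter of the same overall size would look alike. The two could mean different things for predicting response in tumor (section 2.1) and toxicity in background liver (section 2.2). The Bland-Altman comparison is where the offset would appear, and its signed outputs are not written down.

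**Working it through.** **Inputs.** From section 3.2: the multiplier 2.77, one value per modality per subject, and a chi-square bound with N degrees of freedom. From section 3.1: 12 new cases, the 5% limit and the table of bounds. From the Protocol Summary: 8 pilot cases, so 20 if pooled. From section 1.3: first-pilot mean -36%, SD 43%. The bias and SD pairs in steps 3 to 5 are assumptions for illustration, with normal percent differences relative to the PET/CT dose.

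**1. The plan's own table.** Upper bound = RDC × √(N / χ²), with χ² the 5th percentile on N degrees of freedom. At N = 12 the percentile is 5.226, so the factor is √(12/5.226) = 1.515. For RDC = 2, 3, 4 and 5% this gives 3.03, 4.55, 6.06 and 7.58. The table has 3.0, 4.5, 6.1 and 7.6. The rows for 10 and 15 cases also reproduce to rounding.

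**2. What the RDC contains.** With two values differing by d, a subject's variance is d²/2. In population terms:

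RDC = 2.77 × √((bias² + SD²)/2) = 1.959 × √(bias² + SD²).

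- RDC = 5% gives √(bias² + SD²) = 5/1.959 = 2.553, so |bias| cannot exceed 2.55 percentage points.
- If the first pilot's figures are read as percent differences, 1.959 × √(36² + 43²) = 109.8%. A deficit of that size could not pass.

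**3. Two patterns with the same RDC of 5.0%.** Case B borrows the only bias-to-SD ratio in the documents, 36/43 = 0.837, so SD = 2.553/√(1 + 0.837²) = 1.957 and bias = -0.837 × 1.957 = -1.639.

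| | Case A | Case B |
|---|---|---|
| Bias (%) | 0 | -1.64 |
| SD (%) | 2.55 | 1.96 |
| Limits of agreement, bias ± 1.96 SD (%) | -5.0 to +5.0 | -5.5 to +2.2 |
| Share below -5% | 2.5% | 4.3% |
| Share above +5% | 2.5% | 0.03% |

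The RDC alone does not tell these cases apart. The usual Bland-Altman outputs do.

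**4. Does the stated 95% reading of the RDC need a zero mean difference?** Hold the RDC at 5% and add both tails beyond ±5%.

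| abs(bias)/SD | Total beyond ±5% |
|---|---|
| 0 | 5.0% |
| 0.5 | 4.9% |
| 0.837 (Case B) | 4.3% |
| 1 | 3.8% |
| 2 | 0.9% |
| 3 | 0.1% |

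To rounding, the total never exceeds 5.0% over ratios from 0 to 3. Bias changes how the exceedances split between the sides, but the 95% statement survives.

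**5. Could the ordinary outputs be estimated from these data?** The 95% t-interval for the mean difference has half-width t × SD/√N: 2.201/√12 = 0.635 SD at N = 12 and 2.093/√20 = 0.468 SD at N = 20. With sample values equal to Case B, the interval is -2.9 to -0.4 at N = 12 and -2.6 to -0.7 at N = 20. In Case A it is ±1.6 and ±1.2. The same scans therefore support a useful signed estimate.

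**The case for a change.** The best case for a change is that naming Bland-Altman does not settle everything. The direction of subtraction, the scale (Gy or percent), and whether intervals accompany the mean difference and the limits are all unstated, while the RDC's formula and interval are written out. The chi-square bound with N degrees of freedom is also exact, for normal differences, only when the mean difference is zero; the mean difference would let a reader check that. The remedy would cost a sentence or two and no extra scans.

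The observation that these details are not listed stands. Little follows from it:

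- **Direction.** Section 1.2 treats PET/CT as the reference, so PET/MR minus PET/CT is the natural difference.
- **Scale.** The endpoints are in Gy, and section 3.2 also expresses the RDC as a percentage of the PET/CT dose, so the plan already points to both.
- **The bound.** In Case B at N = 12 its coverage is 96.3% against a nominal 95%. The departure is on the safe side.
- **Late choice of analysis.** The method, endpoints, formula and bound are all set before the data are seen. What remains open is presentation.

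Case B also carries a pre-upgrade ratio over to an RDC about 22 times smaller (109.8/5). The upgrades addressed attenuation and motion correction, so nothing in the documents indicates that the ratio persists.

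**Conclusion.** No change to the plan follows. The signed mean difference, the limits of agreement and their intervals are indeed not written out in section 3.2. That section does commit to a cited, standard method for examining the pattern of differences, and the mean difference and limits are its ordinary products. An analyst following the plan would report them. Listing them would add detail without replacing a wrong rule or figure.

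The stakes are small. The RDC, its upper bound and the comparison with 5% would be the same either way, and no stated decision depends on the sign of the difference. A true RDC at the limit already confines bias to 2.55 points in either direction. An observed RDC of 5.0% at N = 12 has an upper bound of 7.58%, which confines it to 7.58/1.959 = 3.9 points. The plan's 95% reading of the RDC holds with or without bias.

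This rests on three assumptions: one value per modality per subject, approximately normal percent differences for the tail figures, and a report that shows the Bland-Altman results and not the RDC alone. If the authors revise the text for another reason, they could list the usual outputs in Gy and in percent, for tumor, background liver and volumetry, and say whether they cover the 12 new cases, the pooled 20 or both. That is optional.
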